4.14.8 Adverse Events

During each visit, participants will be asked about adverse events. All adverse events will be recorded in an ongoing adverse event log. Recording of symptom changes is only necessary when treatment is initiated or when the clinician identifies an unusual rate of change. In the immediate arm, there will be an additional telephone visit led by Clinical Nurse Specialists (CNS) or a delegated medical professional, at 3 and 15 months to ask about adverse events that may require discussion with the PI or SI. A researcher will conduct the telephone visits at 9 and 21 months. Within the delayed arm, there will be a parallel researcher-led telephone visit at 3, 9 and 21 months, with a telephone visit at 15 months led by a CNS or delegated medical professional. All telephone check-ins will follow a standardised proforma with clear guidance on escalation to clinical staff if any concerns arise. This ensures consistency in data collection and participant safety, while allowing flexibility in staffing.

The measures included at each assessment point will assess several adverse events (AE) experienced since the last assessment. Systematic enquiry will include, for birth-registered females, breakthrough menstrual bleeding. All participants will be asked about severe and persistent headaches, galactorrhoea, significant weight changes, unexplained pain, persistent nausea or vomiting, and any other physical symptoms that significantly impact the participant's daily functioning. These physical events will be assessed for their severity and potential relation to the study intervention, and appropriate medical interventions will be provided as necessary.

Follow ups will include suicidal thoughts, suicidal behaviour, a marked increase in the severity of anxiety or depression symptoms, defined as T-score on RCADS subscales >80 when previously lower, increased mental distress requiring unplanned clinical appointments and/or A&E attendances. They will also include detailed information on the child's height and weight, prescribed medications, new diagnoses (both neurodevelopmental and mental health, as well as physical health), and the number of GP appointments attended in the past year. It will also cover any planned surgeries or procedures, A&E visits, reasons for these visits, and whether they led to overnight admissions.

Any hospital admission for an overnight stay will be recorded as a serious adverse event (SAE).

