8.1 Side effects commonly reported

The following side effects are known to be commonly reported to Endocrinology Clinicians that have prescribed Triptorelin for those under the age of 18 years with a diagnosis of “Gender Incongruence” or “Gender Dysphoria” for the indication of puberty suppression. These have been collated from the expert endocrine panel as previously defined.

Common side effects reported clinically include unexpected PV bleeding (commonly referred to as spotting), hot flushes, increased perspiration, weight gain, injection site pain, mood changes, interrupted sleep, low mood, dizziness, fatigue, cyclic menstrual-like pelvic discomfort, breast tenderness, nausea, headache, reduced libido, and loss of spontaneous erections.

Common side effects reported of a subcutaneous injection are localised pain, swelling, sterile abscess, allergic reaction, muscular pain, induration and erythema.

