8.3 Uncommon and rare side effects of Triptorelin

Uncommon is defined as per the BNF and BNFc standards with the frequency of between 1 in 1000 to 1 in 100. Rare is defined as a frequency between 1 in 10000 and 1 in 1000.

In under 18's, uncommon side effects are anaphylactic reaction, haemorrhage, nausea, vaginal discharge and vomiting.

Idiopathic intracranial hypertension (pseudotumor cerebri) has been reported in paediatric patients receiving the IMP. Participants will be counselled to look out for signs and symptoms of idiopathic intracranial hypertension, including severe or recurrent headache, vision disturbances and tinnitus. If suspected, the PI or delegated clinicians should make an urgent referral to ophthalmology.

In adults, uncommon side effects are alopecia, abnormal appetite, exacerbations of asthma, chills, confusion, constipation, diarrhoea, drowsiness, dyspnoea, flatulence, gout, muscle weakness, altered taste, testicular disorders, tinnitus, vertigo, vision disorders and vomiting.

In adults, rare side effects are abnormal eye sensation, chest pain, difficulty standing, fever, hypotension, influenza like illness, musculoskeletal stiffness, nasopharyngitis, orthopnoea, osteoarthritis and QT prolongation.

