9.2 Evaluating AEs and SAEs

Assessment of intensity

The PI or SI will assess intensity for each AE and SAE reported during the study. The assessment will be based on the PI/SI's clinical judgement. The intensity of each AE and SAE recorded in the eCRF should be assigned to one of the following categories:

- **Mild**; An event that is easily tolerated by the participant, causing minimal discomfort and not interfering with everyday activities
- **Moderate**; An event that is sufficiently discomforting to interfere with normal everyday activities
- **Severe**; An event, which is incapacitating and prevents normal everyday activities

The electronic version of this document is the latest version. It is responsibility of the individual to ensure that any paper material is the current version. Printed material is uncontrolled documentation.

An AE that is assessed as severe should not be confused with an SAE. Severity is a category utilised for rating the intensity of an event; and both AEs and SAEs can be assessed as severe.

Assessment of causality

The Investigator is obligated to assess the relationship between investigational product and the occurrence of each AE/SAE. The Investigator will use clinical judgment to determine the relationship. Alternative causes, such as natural history of the underlying diseases, concomitant therapy, other risk factors, and the temporal relationship of the event to the investigational product will be considered and investigated.

The causal relationship to the study product assessed by the Investigator (or medically qualified delegate) should be assessed using the following classifications:

- **Not Related:** In the Investigator's opinion, there is not a causal relationship between the study product and the AE.
- **Unlikely:** The temporal association between the AE and study product is such that the study product is not likely to have any reasonable association with the AE.
- **Possible:** The AE could have been caused by the study participant's clinical state or the study product.
- **Likely:** The AE follows a reasonable temporal sequence from the time of study product administration, abates upon discontinuation of the study product and cannot be reasonably explained by the known characteristics of the study participant's clinical state.
- **Definitely:** The AE follows a reasonable temporal sequence from the time of study product administration or reappears when study product is reintroduced.

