9.3 Adverse event processing responsibilities

The sponsor has delegated the delivery of the Sponsor's responsibility for Pharmacovigilance (as defined in Regulation 5 of the Medicines for Human Use (Clinical Trials) Regulations 2004) to the King's Health Partners Clinical Trials Office (KHP-CTO).

KHP-CTO will report SUSARs to the Research Ethics Committee (REC) and Medicines and Healthcare products Regulatory Agency (MHRA). Reporting timelines are as follows:

- SUSARs which are fatal or life-threatening must be reported no later than 7 days after the sponsor is first aware of the reaction. Any additional relevant information must be reported within a further 8 days;
- SUSARs that are not fatal or life-threatening must be reported within 15 days of the sponsor first becoming aware of the reaction.

The CI and KHP-CTO (on behalf of the co-sponsors) will submit a Development Safety Update Report (DSUR) relating to this trial IMP, to the MHRA and REC annually.

The electronic version of this document is the latest version. It is responsibility of the individual to ensure that any paper material is the current version. Printed material is uncontrolled documentation.

The Trial Statistician will report relevant adverse events to the Data Monitoring Committee. Data on non-serious, severe ARs will be captured where causality is assessed as possible, likely, or definitely, and will be included in DMC reports.

10 Toxicity Management

Monitoring and Management of Adverse Events:

Regular Follow-Up: Participants will attend regular follow-up appointments to assess the efficacy and safety of the treatment. These appointments will include monitoring hormone levels, physical development assessments, routine blood tests, DEXA scans, and physical assessments (height, weight, BMI, blood pressure, and puberty staging).

Psychosocial Screening: Psychosocial screening to identify any unmet needs and escalate these to appropriate services.

Adverse Event Reporting: All adverse events will be recorded in the participants' medical notes, study source data worksheets, and the eCRF. Serious adverse events (SAEs) will be reported within 24 hours to the King's Health Partners Clinical Trials Office (KHP-CTO).

Management of Common Side Effects: Common side effects such as depression, altered mood, anxiety, and hot flushes will be monitored and managed according to clinical guidelines.

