Management of Rare Side Effects: Rare side effects such as anaphylactic reactions, haemorrhage, and idiopathic intracranial hypertension will be monitored closely, and treatment will be discontinued if severe cutaneous adverse reactions (SCARs) occur.

Follow-Up of Adverse Events: All adverse events will be followed until resolution, stabilisation, or until the participant is lost to follow-up. Supplemental investigations may be conducted to elucidate the nature and causality of the adverse events.

11 Premature Termination of Trial

The trial may be prematurely discontinued by the Sponsor, Chief Investigator or Regulatory Authority on the basis of new safety information or for other reasons given by the DMEC, PMC, regulatory authority, or ethics committee concerned.

If the trial is prematurely discontinued, active participants will be informed and no further participant data will be collected. The Competent Authority and Research Ethics Committee will be informed within 15 days of the early termination of the trial.

12 Ethics Approval

This protocol and related documents will be submitted for review to Health Research Authority (HRA), REC and MHRA.

PATHWAYS TRIAL, HORIZON INTENSIVE and CONNECT will be conducted in compliance with the principles of the Declaration of Helsinki (1996), the principles of GCP and all of the applicable regulatory requirements (specify current legislation).

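### The named adverse-event prompts in section 4.14.8 do not match the reactions that sections 8.3 and 10 say participants are counselled on or will be monitored for

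*Protocol*

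**What the plan says.** Section 4.14.8 sets up two layers of enquiry. The first is general: "During each visit, participants will be asked about adverse events. All adverse events will be recorded in an ongoing adverse event log". The second is a systematic enquiry with named items. Birth-registered females are asked about breakthrough bleeding. For everyone, "All participants will be asked about severe and persistent headaches, galactorrhoea, significant weight changes, unexplained pain, persistent nausea or vomiting", and the sentence ends with a catch-all: "and any other physical symptoms that significantly impact the participant's daily functioning".

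Other sections say what is to be watched for:

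- Section 10: "Common side effects such as depression, altered mood, anxiety, and hot flushes will be monitored and managed according to clinical guidelines". Among rare effects it says that "haemorrhage, and idiopathic intracranial hypertension will be monitored closely".
- Section 8.3 has participants counselled to look out for "signs and symptoms of idiopathic intracranial hypertension, including severe or recurrent headache, vision disturbances and tinnitus". Section 8.5 repeats this for all GnRHa preparations and adds vomiting.
- Section 8.1 lists reactions commonly reported in this use of the drug, among them "hot flushes, increased perspiration, weight gain, injection site pain, mood changes, interrupted sleep, low mood, dizziness, fatigue".
- Section 9.2 defines the mild grade of adverse event as one that is easily tolerated, "causing minimal discomfort and not interfering with everyday activities".

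**The concern.** The protocol's list of what it will ask about and its list of what it will watch for were evidently not drawn up together. Hot flushes, visual disturbance and tinnitus appear in the second and not in the first. Headache appears in both, but with a narrower qualifier in the enquiry than in the counselling text. The catch-all does not close the gap for milder events, because it reaches only symptoms with a significant effect on daily life, while 9.2 has a grade for events that have no such effect.

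This matters because risk is part of the primary objective (2.4.1) and adverse events are a listed outcome (13.1.7). Participants and site staff know the allocation (2.1.1 and Table 3 in 6.3). A symptom asked about by name is sought in the same way from everyone. A symptom that depends on an open question is sensitive to what the participant or interviewer thinks worth mentioning, and that can differ between someone on the drug and someone waiting for it.

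**Working it through.** No arithmetic in the protocol bears on this point, so the check sets the sections side by side.

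**1. Named prompts against the commitments**

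| Symptom | Where it is to be watched for | Named prompt in 4.14.8 |
|---|---|---|
| Hot flushes | Section 10 (monitored); 8.1; 8.4 | None |
| Visual disturbance | 8.3 and 8.5 (counselling); 8.4 | None |
| Tinnitus | 8.3 and 8.5 (counselling) | None |
| Headache | 8.3 and 8.5: severe or recurrent | Only if severe and persistent |
| Vomiting | 8.5 | Yes, alongside persistent nausea |

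Sections 8.3 and 8.5 together give four signs of intracranial hypertension. Two (headache and vomiting) have a prompt, the headache prompt with a tighter threshold. Two (vision and tinnitus) have none. A headache that recurs but does not persist is one that participants are told to look out for, yet it falls outside the prompt.

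**2. The catch-all against the grading scale**

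The catch-all requires a significant effect on daily functioning. The mild grade in 9.2 is defined by the absence of interference. A mild hot flush or an early visual symptom is therefore outside every named prompt and outside the catch-all. It can still be recorded, but only through another route.

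**3. The other routes, and whether they are the same in both arms**

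- Open question at each visit: present in both arms, with no named content.
- Telephone check-ins at months 3, 9, 15 and 21: both arms, on a standardised proforma whose items the protocol does not give. At month 3 the call is led by a nurse specialist or delegated medical professional in the immediate arm and by a researcher in the delayed arm (4.14.8).
- Review of systems: content not defined. After baseline, Table 4 (immediate arm) schedules it at months 6, 12, 18 and 24. Table 5 (delayed arm) schedules it at months 12, 18 and 24. Up to and including month 12, that is two reviews against one. Table 5 shows questionnaires and the status form at month 6, and neither table has a telephone check-in then. Section 5.2.6 says the delayed arm receives the same monitoring and assessments.
- Section 4.14.8 also limits the recording of symptom changes to the start of treatment or an unusual rate of change. Treatment starts at month 0 in one arm and month 12 in the other.

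So in the first 12 months, which section 2.2 identifies as the comparison of GnRHa with no endocrine treatment, the unnamed symptoms rest on routes with unspecified content, and some of those routes differ by arm.

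**4. Can the effect be sized?**

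Not from the protocol. Section 8.4 puts hot flush and vision disorders in under-18s among effects of unknown frequency, and nothing states what fraction of events an open question would capture. A power or attenuation figure would need invented values for both. If it also assumed equal capture in the two arms, it would leave out the arm-dependent reporting that is the worry.

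**The case against.** The strongest reply is that 4.14.8 already asks everyone about adverse events at every visit and logs all of them. The named list is introduced as what the enquiry will include, so it need not be closed, and a full checklist may well sit in the case report form or the telephone proforma. Saying in section 10 that a reaction will be monitored does not promise a named question for each symptom; the same section describes monitoring through regular follow-up. Headache and vomiting are prompted. New physical diagnoses and A&E attendances with reasons are collected, so a diagnosed case of intracranial hypertension should surface. Between visits the safeguard is the counselling in 8.3, which added visit prompts would not replace. Choosing some prompts plus an open question is a legitimate design.

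Most of this stands, and it rules out two stronger readings. A reader might infer that the unnamed reactions are recorded only if volunteered. The documents do not support that, given the question at each visit, the logging of all adverse events, the catch-all, the proforma and the review of systems. A reader might also infer that intracranial hypertension goes unmonitored. It is partly covered by prompts and by counselling.

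Nor does every reaction in 8.1 need a prompt. By count, nine of its sixteen have none (hot flushes, perspiration, injection-site pain, sleep, dizziness, fatigue, breast tenderness, libido, erections), but asking about all of them is closer to preference than to correcting an error.

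What the reply does not answer is the mismatch itself: the headache qualifier differs between sections, three symptoms that the protocol singles out elsewhere are not named, and the routes left to catch them are undefined and not identical across arms in the first year.

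**Conclusion.** The point holds as an internal inconsistency with a modest consequence. Hot flushes, visual disturbance, tinnitus and recurrent headache are symptoms the protocol says will be monitored or counsels participants to notice, and its named enquiry omits or narrows them. Milder or early events of these kinds may be ascertained less completely than the prompted ones, and possibly unevenly between arms. The direction and size of any resulting bias are unknown.

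This rests on two assumptions: that the proforma and the case report form do not already name these symptoms, which cannot be seen from the protocol, and that the schedule tables are read correctly as to month 6. If the proforma does name them, what remains is to bring the text of 4.14.8 into line with it. Either way it is a minor ascertainment point, worth correcting because the correction is cheap.

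**What to change.** Reconcile 4.14.8 with 8.1, 8.3 and 10:

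- Add hot flushes, visual disturbance, tinnitus and recurrent headache to the named enquiry and to the telephone proforma.
- Ask the same list at the same contacts in both TRIAL arms, whether or not the participant is yet on drug. This includes settling month 6 in the delayed arm, where Table 5 differs from Table 2 and from 5.2.6.
- Take the functioning threshold out of the catch-all and let the mild, moderate and severe grades in 9.2 carry severity.

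This changes only what is asked and recorded, not how any reaction is managed. The cost is roughly a minute or two more per contact (an estimate) and more mild events to enter. The only place it could add a contact is month 6 in the delayed arm, and there the list could be asked alongside the questionnaires already scheduled.

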4.14.9 Concomitant Medications

During each visit, participants will be asked about their current medication, including private prescriptions, over-the-counter medications and supplements. All concomitant medication will be recorded in an ongoing concomitant medication log.

4.14.10 Withdrawal

A withdrawal form must be completed in the event of participant death or where the participant has stopped taking study medication and is no longer prepared to provide

The electronic version of this document is the latest version. It is responsibility of the individual to ensure that any paper material is the current version. Printed material is uncontrolled documentation.

any follow up data or have their caregiver or family doctor provide any follow up data. Where the participant has stopped study intervention but is still being followed for primary outcome data, a withdrawal form should not be completed, but a status update must be recorded in the EDC at each subsequent visit.

Participants who stop the IMP will be followed up for outcomes where possible.

4.15 Laboratory Data

All tests listed below will be performed as per the time points indicated in the schedule of events in Table 2 (section 4.1). In addition, laboratory safety tests may be performed at unscheduled times, if deemed necessary by the PI and abnormal results recorded as an adverse event if clinically significant. Standard local NHS laboratories will be used to perform the tests at each trial site. If samples are requested elsewhere (eg via a community based doctor) the laboratory results report should be requested. Results must be printed and retained with the source data worksheets, after being reviewed and signed by a physician. Where the results indicate an adverse event or medical condition, this should be recorded in the medical history (at baseline) or on the adverse event log if occurring after randomisation.

Clinically significant abnormalities will be reported to the clinical team and discussed with the participant as necessary, as well as being recorded in the medical history form at screening and baseline or the adverse event form post-randomisation.

Individual result values will not be transcribed to the EDC system unless outside the normal range.

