7.1.1 Medrio EDC

A web based electronic data capture (EDC) system will be created in collaboration with the CI and trial analyst(s), using the Medrio system. This will be maintained by the King's Clinical Trials Unit (KCTU) and Medrio for the duration of the project. It will be hosted on secure servers by Medrio in the EU.

The CI or delegate (e.g., Trial Manager) will request email usernames and passwords from KCTU for new staff members joining the study and will request access removal when staff members leave the project. EDC access is strictly restricted through user-specific passwords to the authorised research team members. It is a legal requirement that passwords to the EDC are not shared, and that only those authorised access the EDC.

Site staff experiencing issues with the EDC system should contact the CI or delegate (e.g., Trial Manager). Medrio training videos are available at www.ctu.co.uk under 'Resources – Events & Training' tab.

Laboratory results may be reviewed directly in hospital laboratory systems where appropriate and need not be transcribed in full to the source data work. Any abnormal results must be recorded and transcribed in the EDC system as an adverse event. Normal results need not be transcribed.

The TM will provide Source Data Worksheets (SDWs) to recruiting sites following completion of database testing. Participating Sites will complete source data location lists defining the source data at their site.

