13.1.6 Continuous Physical Measures

- a) Height (cm)
- b) Weight (kg)
- c) BMI
- d) Bone mineral density (DEXA) z score
- e) Blood pressure; systolic, diastolic, mean
- f) Safety bloods

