13.5.2.1.1 Trial

Continuous secondary outcomes will be analysed using the same estimand using the treatment policy intercurrent event handling method. The same method of analysis will also be used, maintaining the same fixed and random effect structure as the primary outcome analysis. Uninformative priors will also be used for parameters that are to be estimated.

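### Only out-of-range laboratory values enter the trial database, yet safety bloods are planned as a continuous outcome in a baseline-adjusted mixed model

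*Protocol*

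**What the plan says.** Data capture. Section 4.15 (Laboratory Data): "Individual result values will not be transcribed to the EDC system unless outside the normal range". Section 7.1.1 (Medrio EDC): "Any abnormal results must be recorded and transcribed in the EDC system as an adverse event. Normal results need not be transcribed". Results are printed, signed by a physician and filed with source worksheets at site (4.15), or reviewed in hospital laboratory systems (7.1.1). Local NHS laboratories do the testing. Section 7.1 names three TRIAL datasets (Medrio EDC with ePRO, the randomisation system and Q-Interactive) and a separate Medrio database for HORIZON INTENSIVE. None is a laboratory transfer.

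Analysis. Section 13.1.6 lists "Safety bloods" among the continuous physical measures for TRIAL, and Section 13.2.6 does the same for HORIZON INTENSIVE. Section 13.5.2.1.1 says: "Continuous secondary outcomes will be analysed using the same estimand using the treatment policy intercurrent event handling method". It keeps the fixed and random effects of the primary analysis, which include the baseline score (13.5.1.1). Section 13.5.2.1.2 carries the approach over to HORIZON INTENSIVE. Section 13.9 relies on missing data being ignorable.

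Adverse events. On unscheduled tests, Section 4.15 has "abnormal results recorded as an adverse event if clinically significant", and its general paragraph on abnormalities also speaks of clinically significant ones. Section 7.1.1 sets no such threshold.

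**The concern.** A rule that enters a value only when it lies outside the reference range, and a plan to compare means of that same value between arms, cannot both stand. The analysis set would be selected on the outcome. Missing at random requires that, given the observed data, missingness does not depend on the unobserved value. Here the unobserved value is what decides, so the assumption fails by design and not through dropout.

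The baseline term has the same problem. A participant whose baseline result is in range has no baseline value in the database, which for most analytes would be most participants.

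At stake are the arm comparisons of the panel mandated at follow-up in Section 4.15.1.1 (for example lipids, bone profile, prolactin, renal profile). These are collected by repeated blood draws in children, in a trial whose primary objective (2.4.1) covers risks as well as benefits. A naive analysis of what was entered would be misleading, not merely imprecise.

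**Working it through.** The protocol states no figure for this point, so there is none to reproduce. The argument is textual; the arithmetic only gives its scale.

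**1. Can in-range values reach the analysis?** Section 4.15 rules entry out. Section 7.1.1 says it is not needed. Section 7.1 lists no other route. An SAP (none was available for this review) can define summaries, but it cannot analyse values that the protocol keeps out of the database.

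**2. Scheduled TRIAL follow-up values per mandated analyte, before dropout.** Inputs: 113 per arm (Table 1), and the safety-bloods rows of the schedules.
- Tables 4 and 5 (Appendix A): immediate arm at months 6, 12, 18 and 24; delayed arm at months 12, 18 and 24. 113 × 4 + 113 × 3 = 452 + 339 = 791.
- Table 2, to which Section 4.15 refers, and the 6-monthly mandate in Section 4.15.1.1: months 6, 12, 18 and 24 in both arms. 226 × 4 = 904.

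The schedules differ on a month-6 draw in the delayed arm, so both counts are carried. HORIZON INTENSIVE draws (baseline and month 24) are not counted.

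**3. Values entered.** The out-of-range share is not in the protocol. Assume 2% to 20%:
- 791 × 0.02 = 15.8 and 791 × 0.20 = 158.2
- 904 × 0.02 = 18.1 and 904 × 0.20 = 180.8

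So about 16 to 181 values per analyte over all follow-up visits. This range is not meant for LH, FSH, oestradiol or testosterone in treated participants, where suppression may put many values out of range.

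**4. What selection does to a mean difference (illustration).** Assume a normally distributed analyte in SD units, a reference range of ±1.96 SD, and a true shift μ in one arm. With c = 1.96:
- share entered: p(μ) = Φ(−c − μ) + 1 − Φ(c − μ)
- mean of entered values: m(μ) = μ + [φ(c − μ) − φ(c + μ)] / p(μ)

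With no shift, p = 0.050 and m = 0, or 113 × 0.050 = about 5.6 values per arm and visit.

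| True shift (SD) | Share entered, shifted arm | Values entered, unshifted vs shifted arm (of 113 each) | Apparent difference (SD) |
|---|---|---|---|
| 0.2 | 0.0546 | 5.6 vs 6.2 | 1.04 |
| 0.5 | 0.0791 | 5.6 vs 8.9 | 1.99 |
| 1.0 | 0.1701 | 5.6 vs 19.2 | 2.45 |

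**5. Participants with both a baseline and a follow-up value entered.** Same assumptions, no shift, bivariate normal. The probability that both are out of range is 0.0025 at correlation 0, 0.0093 at 0.5 and 0.0219 at 0.8. Multiplied by 226, that is 0.6, 2.1 and 5.0 participants. A baseline-adjusted model could hardly be fitted for such an analyte.

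**The case against.** The strongest reply is that nothing is destroyed. In-range results remain as signed source or in hospital systems, and Section 7.1.1 is permissive where Section 4.15 is categorical, so values could be retrieved before database lock. That stands and limits the seriousness. But no retrieval is planned, and collecting values later from several local laboratories, with their own units and ranges, is harder than prospective entry.

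A second reply is that these are only safety checks. Individual safety does look protected: a physician reviews and signs results, and clinically significant abnormalities go to the clinical team. If that is their only purpose, they should not be listed as a continuous outcome.

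Three stronger readings are tempting but not supported.
- *Hormone suppression could not be described at all.* Suppressed values outside the local range would be entered. The fair statement is that suppression could not be described without selection. How much is lost depends on local age- and sex-specific ranges, which the protocol does not give.
- *Expected suppression would generate adverse events by design and distort the adverse-event outcome.* The two sections do conflict on when an abnormal result is an adverse event. However, Section 9 defines an adverse event as an untoward occurrence, so it is conjecture that intended suppression would be logged as one. This claim also pulls against the previous one: it needs suppressed values to be out of range, in which case they are entered.
- *About 95% of all values would be lost.* That rests on an assumed 5% out-of-range rate, which does not suit hormones in treated participants.

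**Conclusion.** The conflict is real and rests on the text alone. As written, the planned continuous analysis of safety bloods would use a sample selected on the outcome, would breach the assumption in Section 13.9, and would lack a baseline value for most participants on analytes that usually lie in range. Mean arm differences could not be validly estimated from the planned database.

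The size is uncertain. Of 791 or 904 scheduled follow-up values per mandated analyte, about 16 to 181 would be entered if 2% to 20% are out of range. The inflation figures further assume normality and a central 95% reference range and are illustrative. The conclusion depends on none of these.

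This should be fixed but does not threaten the trial's main result. KIDSCREEN-10 is unaffected, bone density comes from DEXA, and individual safety review does not depend on entry in the database. The conflicting adverse-event wording is a separate, smaller point.

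**What to change.** Amend Sections 4.15 and 7.1.1 so that every scheduled numeric result of the mandated panel, at baseline and each follow-up, in TRIAL and HORIZON INTENSIVE, is entered or electronically transferred with its units and local reference range. The cost is data-entry time or a laboratory export, plus an EDC form change; no extra samples are needed. It is cheapest before data accrue.

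If values will not be captured, remove safety bloods from the continuous outcomes in Sections 13.1.6 and 13.2.6 and the synopses, and report counts of out-of-range results. This costs only a text change but gives up the comparison of means.

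Separately, reconcile the adverse-event wording of Section 4.15 with that of Section 7.1.1 so that sites have one rule. Which rule applies is for the sponsor and investigators to decide.
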